#### 11.4.9. Nicotine Use Information

Information regarding the subject's nicotine use will be recorded in the eCRF. Data collected will include the type of nicotine used, approximate amount and time period during which nicotine was / is being used.

#### 11.5. Pharmacokinetic Assessments

All blood samples for determination of plasma SEP-363856 concentrations will be obtained at the same time that other blood samples are taken whenever possible. Date and time of sample collection as well as date and time of the previous dose of study drug prior to pharmacokinetic (PK) blood sampling must be recorded. Plasma SEP-363856 concentrations will be determined by a validated liquid chromatography-tandem mass spectrometry (LC-MS/MS) method. POPPK analysis will be performed using plasma SEP-363856 concentrations; the results of which will be reported separately. The relationship between PANSS total score and plasma SEP-363856 exposure will be explored using population PK/pharmacodynamics (PD) methods and reported

separately. See Section 22, Appendix III for details including instructions of processing blood samples for plasma.

Plasma samples collected for PK concentration analysis

# 11.6. Study Visits and Assessments

See Table 2, for a summary of procedures at each study visit. See Section 11.1 to Section 11.6.10 for detailed information on conducting assessments.

It is suggested that rating scales be completed in the following sequence, if possible. If the sequence must be changed, it is strongly suggested to complete the CGI-S and CGI-I scales after the other clinician-rated scales. The Investigator is encouraged to maintain the same sequence across visits for individual subjects.

1. PANSS
2. BNSS
3. C-SSRS
4. SAS/BARS/AIMS
5. PSP
6. Healthcare resource utilization (HRU)
7. CGI-S
8. CGI-I
9. PSQI
10. SF-12
11. MSQ

Note: Rating assessments will be performed by the rater or subject using an electronic tablet. In the event that the electronic tablet is not available or assessment not available on the tablet, the rating assessments will be performed by the rater or subject using a paper version of the assessment.

# 11.6.1. Visit 1E: Open-Label Extension Baseline (Day 1) – Treatment Period

Visit 1E (Open-label Baseline visit) of the present study is on the same day as the EOT Visit of Study SEP361-308. Subjects will be evaluated at this visit to determine their eligibility for the study. The following procedures will be conducted during this visit:

- Obtain signed informed consent and privacy authorization (if applicable or required by local law) from the subject before conducting any other visit procedures.
- Review inclusion and exclusion criteria
- Concomitant medication review
- Adverse events monitoring
- Dispense study drug

The following procedures conducted in the Core study (SEP361-308) EOT Visit do not need to be repeated for the Open-label extension Baseline visit of this study (SEP361-309):

- Physical and neurological examinations
- Collect nicotine use information
- Vital sign measurements
- Weight (including BMI)
- Waist circumference
- 12-lead ECG
- Fasted blood samples for clinical laboratory evaluation (hematology and serum chemistry)
- Blood sample for PK
- Blood sample for pregnancy test (β-hCG) for female subjects
- Urine sample for UDS and rapid urine drug screen
- Urine sample for rapid urine pregnancy testing
- PANSS
- BNSS
- CGI-S
- CGI-I
- C-SSRS
- SAS
- BARS
- AIMS
- PSQI
- PSP
- SF-12
- MSQ
- HCRU

# 11.6.2. Visit 2E (Week 4; Day $29 \pm 3$ ) – Treatment Period

- Collect concomitant medications
- Physical and neurological examinations
- Vital sign measurements

- Weight and waist circumference (BMI derived in the electronic data system)
- Perform standard 12-lead ECG
- Fasted blood samples for clinical laboratory evaluation (hematology and serum chemistry)
- Blood sample for PK
- Urine sample for urinalysis, UDS, and  $\beta$ -hCG (for female subjects)
- PANSS
- CGI-S
- CGI-I
- BNSS
- C-SSRS
- SAS
- BARS
- AIMS
- Collect adverse events
- Study drug accountability
- Dispense study drug

# 11.6.3. Visit 3E (Week 8; Day $57 \pm 3$ ) – Treatment Period

- Collect concomitant medications
- Vital sign measurements
- Weight (BMI derived in the electronic data system)
- Urine sample for  $\beta$ -hCG (for female subjects)
- PANSS
- CGI-S
- CGI-I
- BNSS
- C-SSRS
- Collect adverse events
- Study drug accountability
- Dispense study drug

## 11.6.4. Visit 4E (Week 12; Day $85 \pm 3$ days) – Treatment Period

The following procedures will be conducted during this visit:

- Collect concomitant medications
- Physical and neurological examinations
- Collect nicotine use information
- Vital sign measurements
- Weight and waist circumference (BMI derived in the electronic data system)
- 12-lead ECG
- Fasted blood samples for clinical laboratory evaluation (hematology and serum chemistry)
- Blood sample for PK
- Urine sample for pregnancy test (β-hCG) for female subjects
- Urine sample for UDS
- C-SSRS
- PSQI
- PSP
- HCRU
- Collect adverse events
- Study drug accountability
- Dispense study drug

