**Table 2: Schedule of Assessments** 

Procedures			Tre	atment Per	iod			Follow-up Period
	V1E	V2E	V3E	V4E	V5E	V6E	V7E	V8E
	OLE Baseline a	Week 4	Week 8	Week 12	Week 16	Week 20	Week 24 EOT/ ET b	Follow-up EOS c
Study Day	Day 1	Day 29 ±3 days	Day 57 ±3 days	Day 85 ±3 days	Day 113 ±3 days	Day 141 ±3 days	Day 169 ±3 days	7±2 days after last dose
Informed consent	X							
Inclusion/exclusion criteria	X							
Concomitant medication review d	X	X	X	X	X	X	X	X
Dispense study drug e	X	X	X	X	X	X		
Study drug accountability		X	X	X	X	X	X	
Telephone contacts f			duled visits					
Physical/neurological examination	Core	X		X			X	X
Nicotine use information	Core			X			X	
Vital signs g	Core	X	X	X	X	X	X	X
Weight (including BMI h)	Core	X	X	X	X	X	X	
Height i	Core Pre- switch screening							
Waist circumference	Core	X		X			X	
12-lead Electrocardiogram (ECG)	Core	X		X			X	
Hematology, chemistry, urinalysis j	Core	X		X			X	
Blood sample for PK k	Core	X		X			X	
Urine drug screen 		X		X			X	
Rapid urine drug screen 	Core							
Serum β-hCG, females only	Core							
Urine β-hCG, females only m		X	X	X	X	X	X	X
Rapid urine β-hCG, females only m	Core							
Positive and Negative Syndrome Scale (PANSS)	Core	X	X		X		X	
Clinical Global Impression – Severity (CGI-S)	Core	X	X		X		X	

**Table 2:** Schedule of Assessments (Continued)

Procedures			Tre	atment Peri	iod			Follow-up Period
	V1E	V2E	V3E	V4E	V5E	V6E	V7E	V8E
	OLE Baseline a	Week 4	Week 8	Week 12	Week 16	Week 20	Week 24 EOT/ ET b	Follow-up EOS c
Study Day	Day 1	Day 29 ±3 days	Day 57 ±3 days	Day 85 ±3 days	Day 113 ±3 days	Day 141 ±3 days	Day 169 ±3 days	7±2 days after last dose
Clinical Global Impression – Improvement (CGI-I)	Core	X	X		X		X	
Brief Negative Symptom Scale (BNSS)	Core	X	X		X		X	
Columbia Suicide Severity Rating Scale (C-SSRS)	Core	X	X	X	X	X	X	X
Simpson-Angus Scale (SAS) n	Core	X					X	
Barnes Akathisia Rating Scale (BARS) n	Core	X					X	
Abnormal Involuntary Movement Scale (AIMS) n	Core	X					X	
Pittsburgh Sleep Quality Index (PSQI)	Core			X			X	
Personal and Social Performance Scale (PSP)	Core			X			X	
Short Form Health Survey (SF-12)	Core						X	
Medication Satisfaction Questionnaire (MSQ)	Core						X	
Healthcare Resource Utilization (HCRU), since last assessment	Pre-switch Baseline visit of Core			X			X	

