Adverse events (AE) monitoring °	X	X	X	X	X	X	X	X

Abbreviations: AE = adverse event; BARS = Barnes Akathisia Rating Scale; β-hCG = human chorionic gonadotropin; BMI = Body Mass Index; BNSS = Brief Negative Symptom Scale; C-SSRS = Columbia Suicide Severity Rating Scale; eCRF = electronic case report form; EDC = electronic data capture; EOS = end of study; EOT = end of treatment; ET = early termination; HCRU = healthcare resource utilization; MSQ = Medication Satisfaction Questionnaire; OLE = open-label extension; PANSS = Positive and Negative Syndrome Scale; PK = pharmacokinetic; PSP = Personal and Social Performance Scale; SAS = Simpson-Angus Scale; SF-12 = Short Form Health Survey.

<sup>a The Week 8 (EOT) visit of Study SEP361-308 serves as the Baseline visit for the present study. "Core" indicates assessments that were conducted at the EOS Visit of Study SEP361-308, unless otherwise indicated, and do not need to be repeated for this study.

<sup>b If a subject discontinues from the study, all ET procedures should be performed at the ET visit, within 48 hours of last study dose.

- c All subjects should have a safety Follow-up Visit 7 (± 2) days after their last dose of study drug. While every effort should be made to complete the Follow-up Visit in the clinic, administration of the C-SSRS, and collection of AEs and concomitant medications may occur by telephone contact if the subject is unable to come to the clinic for the Follow-up Visit.
- d Medications with onset during the Core study (SEP361-308) and ongoing at the start of the current study (SEP361-309) will be entered into the eCRF.
- e All study drug will be taken once daily in the evening at bedtime by mouth, with or without food.
- f Telephone calls will be made by a qualified member of the research staff to the subject **weekly** between scheduled study visits to administer the C-SSRS, collect AEs and concomitant medications, as well as to remind the subject about adherence to study drug administration and upcoming visits.
- g Vital signs will include respiratory rate, oral body temperature and supine and standing measurements of blood pressure and pulse rate.
- h BMI will be derived in the EDC system and during statistical analysis.
- i Height collected at the Core study (SEP361-308) Screening Visit will be re-entered into EDC at Visit 2E of this study.

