## **6.2.** Other Safety Endpoints

- Observed values and changes from Baseline of Study SEP361-308 (pre-switch baseline [PS Baseline]) and Baseline of Study SEP361-309 (open-label extension [OLE] Baseline) in clinical laboratory tests (including hematology, chemistry [including but not limited to lipid parameters and Hemoglobin A1c (HbA1c)], and urinalysis) (See Section 21)
- Observed values and changes from PS Baseline and OLE Baseline in vital signs (including temperature, body weight, body mass index [BMI], waist circumference, blood pressure [supine and standing], pulse rate [supine and standing] and respiratory rate) and 12-lead ECG parameters
- Frequency of subjects with suicidal ideation and suicidal behavior based on the C-SSRS
- Change from PS Baseline and OLE Baseline in SAS, BARS and AIMS scores
- Change from PS Baseline and OLE Baseline in PSQI scores

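### Table 2 schedules a urinalysis at Week 12, but the Section 11.6.4 procedure list for that visit leaves it out

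*Protocol*

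**What the plan says.** **Schedule.** Table 2 combines three laboratory groups in one row, "Hematology, chemistry, urinalysis". The row reads Core at the OLE Baseline (Visit 1E) and X at Week 4 (Visit 2E), Week 12 (Visit 4E) and Week 24/EOT/ET (Visit 7E).

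**Visit lists.** Section 11.6.4 sets out the procedures that will be conducted at Week 12. Its laboratory line is "Fasted blood samples for clinical laboratory evaluation (hematology and serum chemistry"). Its urine items are a pregnancy test for female subjects and "Urine sample for UDS". Urinalysis does not appear. The lists for Week 4 (Section 11.6.2) and Week 24/EOT/ET (Section 11.6.7) contain the same blood line and add one that begins "Urine sample for urinalysis, UDS, and" and ends with the pregnancy test.

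**Use of the data.** Section 6.2 makes "Observed values and changes from Baseline of Study SEP361-308 (pre-switch baseline [PS Baseline]) and Baseline of Study SEP361-309" an other safety endpoint for clinical laboratory tests and names urinalysis among them. Section 15.3.6.3 plans shift tables and by-visit summaries, with change from both baselines.

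**The concern.** Sites have two instructions for the same visit, and they differ. A site that follows Table 2 takes a Week 12 urinalysis. A site that follows the Section 11.6.4 list does not, and each can claim to have followed the protocol. With approximately 24 sites planned, collection could vary by site.

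At stake are the Week 12 column of the urinalysis summaries, the corresponding change values and shifts, and the only scheduled look at urinalysis in the long middle stretch of a study whose purpose is long-term safety. A sample that was never taken cannot be recovered at the analysis stage.

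**Working it through.** The check is a visit-by-visit comparison of Table 2 with the lists in Section 11.6. The plan states no figure on this point, so there is none to reproduce.

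| Visit | Table 2, urinalysis | Section 11.6 list, urinalysis | Agree? |
|---|---|---|---|
| 2E, Week 4 | X | named (11.6.2) | yes |
| 3E, Week 8 | blank | not named (11.6.3) | yes |
| 4E, Week 12 | X | **not named (11.6.4)** | **no** |
| 5E, Week 16 | blank | not named (11.6.5) | yes |
| 6E, Week 20 | blank | not named (11.6.6) | yes |
| 7E, Week 24/EOT/ET | X | named (11.6.7) | yes |

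**Could urinalysis be implied at Week 12?** The blood line covers blood only, and its parenthesis is limited to hematology and serum chemistry. The Week 4 and Week 24 lists use that line and still add urinalysis as a urine item. Appendix II (Section 21) sets urinalysis apart from hematology and blood chemistries. So the Week 12 list does not include it by implication.

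**Does the protocol say which source governs?** The synopsis says the procedures outlined in Table 2 will be conducted. Section 7.1 points to Table 2 and Section 11.6 together. Section 11.6 calls Table 2 a summary and sends the reader to Sections 11.1 to 11.6.10 for detail. None of these ranks one above the other.

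**Size.**
- On-treatment urinalyses: Table 2 gives 3 (Weeks 4, 12, 24); the Section 11.6 lists give 2 (Weeks 4, 24). At risk: 3 − 2 = 1 of 3, or 33%.
- Interval without a scheduled urinalysis if Week 12 is missed: 24 − 4 = 20 weeks (Day 29 to Day 169, 140 days).
- Ceiling on samples: anticipated enrollment is 120 × 0.75 × 0.75 = 67.5, stated as approximately 67. About 67 Week 12 samples would be lost only if every enrolled subject reached Week 12 and every site ignored Table 2.

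**The case against.** The strongest reply is that Table 2 is itself operative and cited repeatedly (synopsis, Sections 7.1, 11 and 11.6), that Section 11.3.2 says urine will be collected for laboratory tests and refers to the central laboratory manual, and that sites commonly work from the schedule table. This stands as far as likelihood goes: it is wrong to say that sites will lose the sample, and the 33% and 67-sample figures are ceilings, not expected losses. It does not remove the conflict, because a list of what will be conducted at the visit omits something the table requires.

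It is also fair that the consequence is small. Urinalysis is one component of one descriptive safety endpoint, and the Week 4 and Week 24/EOT/ET samples are scheduled in both places.

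A reader might go further and infer that the OLE Baseline urinalysis is missing, since Section 11.6.1 does not name it either. The documents do not support that. The longer list in Section 11.6.1 recites procedures from the core study's EOT visit that "do not need to be repeated for the Open-label extension Baseline visit of this study (SEP361-309"); it does not instruct sites to collect anything. Table 2 marks the baseline as Core, which its footnote says "indicates assessments that were conducted at the EOS Visit of Study SEP361-308, unless otherwise indicated". Under either source a site takes no urinalysis at Visit 1E, so site action is the same. Whether the core study took one depends on the SEP361-308 protocol, which is not shown.

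The same applies to the drug screen. Section 11.6.1 lists "Urine sample for UDS and rapid urine drug screen" as done in the core study, while Table 2 marks only the rapid screen as Core. This is a difference about what the earlier study did. Exclusion criterion 3 rests on the rapid screen, which both places list, and the drug screen is not an endpoint.

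**Conclusion.** The conflict at Week 12 is real and should be corrected; its effect is minor. At most 1 of 3 on-treatment urinalyses is at risk, with a gap of up to 20 weeks between scheduled urinalyses at any site that works only from Section 11.6.4. What could suffer is the completeness, and the consistency across sites, of the Week 12 by-visit summary and change values.

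The primary endpoint, the incidence of adverse events, does not use urinalysis values, and the scheduled Week 4 and Week 24/EOT/ET collections are intact. No claim is made that the OLE Baseline value is absent.

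The conclusion assumes that Table 2 shows the intended schedule, which the Week 4 and Week 24 lists support, and that no site instruction outside this protocol has already settled the matter. The number of sites that would follow the list rather than the table is unknown.

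**What to change.** In Section 11.6.4, replace the separate urine lines for the pregnancy test and drug screen with the line used in Sections 11.6.2 and 11.6.7, which begins "Urine sample for urinalysis, UDS, and" and continues with β-hCG for female subjects. Section 11.6.4 then agrees with Table 2.

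The cost is one line of text. Urine is already taken at Week 12 for the drug screen, and Table 6 assigns both the drug screen and urinalysis to the central laboratory, so no new visit or vendor is needed.

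As housekeeping only, align the Section 11.6.1 recital of core-study procedures (urinalysis and drug screen) with the Visit 1E column of Table 2, and use one name for the core-study visit, which the Table 2 footnote calls EOS and Section 11.6.1 calls EOT. This changes nothing that is collected in SEP361-309.

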# 11.6.5. Visit 5E (Week 16; Day 113 $\pm$ 3 days) – Treatment Period

- Collect concomitant medications
- Vital sign measurements
- Weight (BMI derived in the electronic data system)
- Urine sample for β-hCG (for female subjects)
- PANSS
- CGI-S
- CGI-I
- BNSS
- C-SSRS

- Collect adverse events
- Study drug accountability
- Dispense study drug

## 11.6.6. Visit 6E (Week 20; Day $141 \pm 3$ days) – Treatment Period

The following procedures will be conducted during this visit:

- Collect concomitant medications
- Vital sign measurements
- Weight (BMI derived in the electronic data system)
- Urine sample for  $\beta$ -hCG (for female subjects)
- C-SSRS
- Collect adverse events
- Study drug accountability
- Dispense study drug

# 11.6.7. Visit 7E (Week 24 / End of Treatment / Early Termination; Day 169 ± 3 days) – Treatment Period

- Collect concomitant medications
- Physical and neurological examinations
- Collect nicotine use information
- Vital sign measurements
- Weight and waist circumference (BMI derived in the electronic data system)
- Perform standard 12-lead ECG
- Fasted blood samples for clinical laboratory evaluation (hematology and serum chemistry)
- Blood sample for PK
- Urine sample for urinalysis, UDS, and  $\beta$ -hCG (for female subjects)
- PANSS
- CGI-S
- CGI-I
- BNSS
- C-SSRS

- SAS
- BARS
- AIMS
- PSQI
- PSP
- SF-12
- MSO
- HCRU
- Collect adverse events
- Study drug accountability

# 11.6.8. Telephone Contact (Weeks 1, 2, 3, 5, 6, 7, 9, 10, 11, 13, 14, 15, 17, 18, 19, 21, 22, and 23) – Treatment Period

Telephone calls will be made by a member of the research staff to the subject between scheduled study visits at Weeks 1, 2, 3, 5, 6, 7, 9, 10, 11, 13, 14, 15, 17, 18, 19, 21, 22, and 23. The telephone calls will be used to administer the C-SSRS, collect AEs and concomitant medications, as well as to remind the subject about adherence to study drug administration and upcoming visits.

# 11.6.9. Visit 8E ( $7 \pm 2$ days after last dose) - Follow-up Period

All subjects who discontinue early or complete the study will have a safety follow-up visit  $7 \pm 2$  days after their last dose of study drug. While every effort should be made to complete the Follow-up Visit in the clinic, administration of the C-SSRS, and collection of AEs and concomitant medications may occur by telephone contact if the subject is unable to come to the clinic for the Follow-up Visit.

The following procedures will be conducted during this visit:

- Concomitant medications
- Physical and neurological examinations
- Vital sign measurements
- Urine sample for β-hCG (for female subjects)
- C-SSRS
- Adverse events

#### 11.6.10. Unscheduled Visit for Dose Adjustment

If a dose increase or decrease is needed between regularly scheduled visits, the subject must return to the clinic for an unscheduled visit. The following procedures will be conducted during this visit for dose adjustment:

- Study drug accountability
- Dispense study drug
- Adverse event monitoring
- Concomitant medication review

Other assessments are not required at such dose adjustment visits, but are permitted, based on the Investigator's judgment.

#### 12. SAFETY REPORTING

#### 12.1. Definitions

#### 12.1.1. Adverse Events

An adverse event (AE) is any untoward medical occurrence associated with the use of a drug in humans, whether or not considered drug related.

Untoward medical occurrences that occur between the time of signing the ICF and first drug administration are pre-treatment events. Those that occur after first administration of study drug are considered AEs.

An AE can, therefore, be any unfavorable and unintended sign (including an abnormal laboratory finding), symptom, or disease occurring after the administration of a medicinal (investigational) product, whether or not considered related to the medicinal (investigational) product. AEs may include the onset of new illness and the exacerbation of pre-existing conditions. AEs will be collected from the signing of the ICF to the last study visit (including Follow-up Visit).

The Investigator should attempt to establish a diagnosis of the event based on signs, symptoms, and/or other clinical information. In such cases, the diagnosis should be documented as the AE and not the individual signs/symptoms.

If a subject answers "yes" to "Suicidal Ideation" Item 4 (active suicidal ideation with some intent to act, without specific plan) or Item 5 (active suicidal ideation with specific plan and intent) on any post-Baseline C-SSRS assessment, an associated AE must be reported.

#### 12.1.2. Serious Adverse Events

A serious adverse event (SAE) is an AE that meets one or more of the following criteria:

- Results in death.
- Is life threatening.
- Requires hospitalization or prolongation of existing hospitalization.
- Results in persistent or significant disability or incapacity.
- Is a congenital anomaly or birth defect.
- Is an important medical event that may jeopardize the subject or may require a medical or surgical intervention to prevent one of the outcomes listed above. Examples of such medical events include allergic bronchospasm requiring intensive treatment in an emergency room (ER) or at home, blood dyscrasias or convulsions that do not result in inpatient hospitalization.

The term "severe" is often used to describe the severity of a specific event (as in mild, moderate, or severe myocardial infarction) (see Section 12.3); the event itself, however, may be of relatively minor medical significance (such as severe headache). This is not the same as "serious," which is based on subject/event outcome or action criteria usually associated with events that pose a threat to a subject's life or functioning as defined by the criteria above.

During the study, if a subject has a hospitalization or procedure (eg, elective surgery) that was scheduled before the study entry, ie, before informed consent for an event/condition that occurred before the study, the hospitalization is considered a therapeutic intervention and not the result of a SAE. However, if the event/condition worsens during the study, it should be reported as an AE (or SAE, if the event/condition results in a serious outcome such as prolongation of hospitalization).

Life-threatening means that the subject was, in the view of the Investigator, at immediate risk of death from the event as it occurred. This definition does not include an event that had it occurred in a more severe form might have caused death.

SAE criteria information will be captured on the CRF.

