- j Subjects must be fasted (no food or drink except water at least 8 hours prior to clinical laboratory tests). A list of clinical laboratory tests is provided in Section 21.
- k Blood samples for plasma concentrations of SEP-363856 will be collected on Day 29, Day 85 and Day 169/EOT/ET. The time and date of the previous dose of study drug prior to blood sampling and the time and date of blood sampling must be recorded. The remaining plasma samples, after PK measurement is completed, CCI
-  Urine drug screen may be ordered at other visits as deemed clinically appropriate. These results should be discussed with the Medical Monitor.
- m Any positive urine β-hCG test should be confirmed by a serum β-hCG test.
- n Unscheduled SAS, BARS and AIMS scales should be administered if a subject develops extrapyramidal symptoms requiring treatment.
- o Any new AEs occurring after signing the informed consent form for this study (SEP361-309) at V1E will be collected. Adverse events with onset during the Core study (SEP361-308) and ongoing at the start of the current study (SEP361-309) will be entered into the eCRF.

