Switching between antipsychotic medications is common in the treatment of schizophrenia (Faries-2009). There may be many reasons for switching antipsychotic treatment, including unsatisfactory response to current treatment, poor tolerability, comorbid physical and psychiatric conditions, and patient request. Clinically warranted switches can provide benefits by enhancing treatment effectiveness, tolerability, and overall acceptance by patients (Weiden-2003). Studies have shown that up to one-third of outpatients with schizophrenia in the United States switch antipsychotic therapy within one year (Weiden-2006, Buckley-2007). According to most empirically based criteria (Kinon-2000), successful switching paradigms involve gradual discontinuation of the original antipsychotic drug upon initiation of the new treatment. Individual patient characteristics, as well as the binding profile and dose level of the original antipsychotic, can influence the appropriate duration for successful discontinuation (Buckley-2007; Cerovecki-2013; Takeuchi-2018).

In light of the novel mechanism of action of SEP-363856, it is important to understand the safety and effectiveness by which a patient can be switched to SEP-363856 using common methods employed in a clinical outpatient setting.

Therefore, the current 24-week study is an open-label extension to an 8-week, outpatient, multicenter, flexible-dose, single-group study designed to evaluate the effectiveness, safety, and tolerability of switching clinically stable outpatients with schizophrenia, who can potentially benefit from a switch for tolerability or efficacy reasons, from their pre-switch antipsychotic medication to SEP-363856. The open-label extension will provide additional, long-term safety, tolerability and effectiveness data from subjects who completed the 8-week switch trial.

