### 6. STUDY ENDPOINTS

## **6.1.** Primary Endpoint

• The incidence of overall AEs, SAEs, and AEs leading to discontinuation

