### 7. INVESTIGATIONAL PLAN

## 7.1. Overall Study Design

This is a 24-week, outpatient, multicenter, flexible-dose, open-label extension study designed to evaluate the long-term safety and tolerability of SEP-363856 (50 to 100 mg/day) for the treatment of subjects with schizophrenia who have completed Study SEP361-308 treatment period, during which they were switched from a previous antipsychotic treatment to SEP-363856.

The study will consist of two periods: An open-label extension (OLE) Treatment Period (up to 24 weeks), and a Follow-up Period visit at  $7 \pm 2$  days after last study drug dose for subjects who complete the Treatment Period and those who prematurely discontinue from the study (Figure 1).

Subjects who meet the entry criteria and choose to enter the extension study will transition immediately at the End of Treatment (EOT) visit from Study SEP361-308. Subjects who early terminate (ET) from the SEP361-308 study are not eligible to enroll in SEP361-309. The EOT visit from Study SEP361-308 will serve as the OLE Baseline visit for the present study. Informed consent will be obtained from all subjects before any study procedures are performed for the present study.

A study schematic is presented in Figure 1. Details of the study assessments and other procedures to be performed at each visit are presented in Table 2 Schedule of Assessments, and Section 11.6, Study Visits and Assessments. If necessary, subjects may return to the clinic at any time for an unscheduled visit at the discretion of the investigator.

Subjects will attend a Baseline visit on Day 1 (same day as the EOT visit of Study SEP361-308). Subjects will be seen at Baseline and then every 4 weeks thereafter up to Week 24. Telephone calls will be made by a qualified member of the clinical research staff to the subjects weekly between visits to administer the C-SSRS, collect AEs and concomitant medications, as well as to remind subjects about adherence to study drug administration and upcoming visits.

[figure not shown]

Figure 1: Study Schematic

Abbreviations: OLE = open-label extension.

All subjects will begin by receiving open-label SEP-363856 at the same dose they were taking upon completion of Study SEP361-308. Thereafter, the dose can be adjusted within the range of 50 to 100 mg/day, if deemed clinically necessary by the Investigator.

Dose adjustment criteria for SEP-363856 are described in Section 10.1.1.

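### The planned-hospitalization exception is tied to SEP361-309 consent, so it also exempts planned stays for conditions that first arose on SEP-363856 in SEP361-308

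*Protocol*

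**What the plan says.** Protocol section 12.1.2 lists hospitalization among the criteria that make an AE serious. It then makes an exception for a hospitalization or procedure "scheduled before the study entry, ie, before informed consent for an event/condition that occurred before the study". If both parts are met, "the hospitalization is considered a therapeutic intervention and not the result of a SAE". The paragraph sets one limit: "if the event/condition worsens during the study, it should be reported as an AE", or as an SAE if the outcome is serious.

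The study is an "open-label extension to an 8-week, outpatient, multicenter, flexible-dose, single-group study" (section 4.2). Section 7.1 says that subjects "will transition immediately at the End of Treatment (EOT) visit from Study SEP361-308", having been switched to SEP-363856 in that study. Section 11.6.1 says that Visit 1E, where SEP361-309 consent is signed, "is on the same day as the EOT Visit of Study SEP361-308". Under section 10.1.1 subjects carry on with the dose they were taking when the core study ended.

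On recording, a note to Table 2 says: "Any new AEs occurring after signing the informed consent form for this study (SEP361-309) at V1E will be collected". The same note has core-study AEs that are still ongoing entered in the SEP361-309 eCRF. Section 15.3.6.2 keeps those carried-over AEs out of the summary tables and shows them in listings only. Section 12.4.1 requires an SAE to be sent to the sponsor's pharmacovigilance group within 24 hours of awareness.

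**The concern.** In a first study of a drug, consent comes before exposure. An exception that turns on events before consent then removes only conditions the drug could not have caused. In this extension, consent comes after a period of treatment with the same drug, so the same wording reaches conditions that emerged on SEP-363856.

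What is at stake is how individual cases are classified and reported. Long-term safety is the primary objective (section 5.1). A hospital stay during treatment, for a condition that began on treatment, would normally be reported quickly and marked serious. Here the text directs the site not to do so on account of that stay. Carried-over AEs appear only in listings, so no table in this study would show that the serious flag is absent.

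**Working it through.** No arithmetic applies. The protocol states no figure on this point, and the question is what the definition does when it is applied to the rollover timeline.

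**Step 1. Which consent?** Section 12.1.2 equates study entry with informed consent and does not name a study. Table 4 defines an enrolled subject by the study-specific consent, and the Table 2 note places that consent at V1E. Where the protocol means the core study, it says so: the male contraception period in section 10.4 starts at SEP361-308 Screening, and the Table 2 notes name the core study for carried-over AEs and medications. A site would therefore apply the V1E date.

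**Step 2. What has happened by then?** V1E is the Week 8 (end-of-treatment) visit of SEP361-308. Only subjects who completed that study's treatment period may enter, and in it they were switched to SEP-363856. The time before the study therefore includes exposure to the investigational drug.

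**Step 3. Apply the rule.** Each case below is a planned stay that takes place during the extension.

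| Case | Current 12.1.2 | Anchored to SEP361-308 consent and first SEP-363856 dose |
|---|---|---|
| Condition predates the first SEP-363856 dose; stay booked before SEP361-308 consent; no worsening | Exempt | Exempt |
| Condition arose on SEP-363856 in SEP361-308; stay booked before V1E consent; no worsening | Exempt | Serious by the hospitalization criterion |
| As the row above, but the condition worsens in SEP361-309 | AE, or SAE if the outcome is serious | Serious by the hospitalization criterion |
| Condition arises in SEP361-309 | Not exempt | Not exempt |

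The second row is the gap. Both parts of the exception are met, and the worsening limit does not apply.

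**Step 4. Follow the consequences.**
- *Reporting.* Section 12.4.1 applies to SAEs. A stay declared not to result from one does not trigger the 24-hour report. The same section asks for serious events between SEP361-309 consent and the first extension dose to be reported in the same way, so the protocol is stricter about that short interval than about the preceding weeks on drug.
- *Listings.* The AE, if ongoing, is in the eCRF and the listings, but is not marked serious because of this stay.
- *Primary endpoint.* Section 6.1 defines it as "The incidence of overall AEs, SAEs, and AEs leading to discontinuation". Section 15.3.6.2 limits the AE summary to events newly occurring on or after the first extension dose. The second-row event began in SEP361-308, so it is outside the summary whether or not it is flagged serious. The planned SAE proportion is the same under either anchor.

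**The case against.** The best case for leaving the text alone is that little is lost. Ongoing core-study AEs are entered in the eCRF, and section 12.3 has each AE assessed for seriousness and followed to resolution or stabilization. The exception removes only the planned stay as a trigger. The other criteria still apply, including that of an important medical event that may need intervention. Hospitalizations and their length are also collected as healthcare resource use (11.4.8) and summarized (15.3.5.1). The scenario is narrow: a new condition within the core study, not urgent enough to be treated before its end, acceptable to the investigator under the exclusion criteria, and stable afterwards. The protocol also never says that the exception is meant only for conditions that predate the drug.

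Most of this stands as a limit on size. It does not close the gap. Neither eCRF entry nor resource-use data leads to a 24-hour report, and a stable condition with a planned admission need not meet any other criterion. The purpose of the exception is indeed not stated, but its effect follows from the text.

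Two stronger readings should be resisted. A reader might infer that the primary SAE incidence is understated. Section 15.3.6.2 rules that out, because carried-over AEs are not counted; and if the condition worsens, the existing clause already restores reporting. A reader might also infer that the stay is lost between the two studies. That depends on the SAE follow-up rules of SEP361-308, which are not in this document. It can be neither shown nor excluded.

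**Conclusion.** The point holds as a defect in how seriousness is defined and reported at rollover. As written, section 12.1.2 declares a planned stay in the extension not to be the result of an SAE even when the condition first arose on SEP-363856 in SEP361-308, unless the condition worsens or another criterion is met. What is lost is the serious flag in SEP361-309 and the expedited report for that case. The AE itself remains recorded if it is ongoing at the start of the extension.

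The effect on the planned primary proportion is nil. The number of affected subjects cannot be estimated from the protocol; it is likely to be small, and no percentage or interval should be attached to it. The conclusion rests on reading consent in 12.1.2 as SEP361-309 consent, which the rest of the protocol supports. It makes no assumption about what SEP361-308 captures. The text should be changed, because reporting matters case by case and the correction is short.

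**What to change.** Reword the exception in section 12.1.2 so that it applies to a hospitalization or procedure scheduled before informed consent for SEP361-308, for a condition present before the first dose of SEP-363856 in that study. Keep the worsening clause. Add that a hospitalization during SEP361-309 for an event that arose on SEP-363856 in SEP361-308 is reported as serious even if it was booked before SEP361-309 consent, and that the report is linked to the SEP361-308 event record so that the event is not counted twice.

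The cost is a short amendment, a line in site safety training and an occasional extra or cross-referenced SAE report. One side effect should be accepted knowingly: a stay booked during SEP361-308 for a condition that predates the drug would also lose the exemption, because it was not scheduled before SEP361-308 consent. Dosing, visits and the planned analyses do not change, and carried-over AEs can stay in listings only.
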